likelihood estimation will be used to create a composite adherence metric by generating a single factor score from the 5 measures of adherence.

**Regimen Knowledge:** Patient identification of drug names and indication will be assessed via assessments used previously by [name] and colleagues (ref). Patients will be asked about each of these via structured, open-ended items. Understanding of proper dosing will be assessed using the 24 hour recall task described above, but patients will be given credit if they demonstrate knowledge of how to take their medication correctly regardless of their actual behavior. From this assessment, we can also determine how patients are taking their entire multi-drug regimen, and if medications are consolidated in the most efficient manner. We will examine the total number of times throughout a 24 hour period patients indicate they will take medicine.

**Quality of Life.** We will use Patient Reported Outcomes Measurement Information System (PROMIS) Physical Function, Anxiety, Depression and Global Health subscales.

**Clinical Outcomes.** will be collected via EHR by site. Transplant-specific outcomes include: 1) change in estimated glomerular filtration rate (eGFR; ml/mn) over 24 months, 2) *Re-hospitalization*: Acute care hospitalizations 3) *Acute Rejection*: proven biopsy meeting organ-specific Banff criteria; 4) *Toxicity*: related to CNI medications (hypertension; neuro-toxic events); 5) *Infection*: CMV, BKV, bacterial infections assessed by laboratory tests and/or biopsies. *Blood pressure* (continuous SBP; control (y/n): SBP<140 & DBP<90) and *glycemic control (HbA1c)* will also be examined in those with hypertension and diabetes.

[figure not shown]

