**11.0 Data and Specimen Management:**

**11.1 Analysis Plan.**

All analyses will be performed in SAS v9.4 (SAS Institute, Cary, NC). [name] will perform analyses under the direct supervision of Drs. [name], [name] and [name]. Drs. [name] and [name] will also provide guidance.

Aim 1.

The proposed trial uses a 1:1 randomized design that assigns patients to TAKE IT or usual care within each cohort. We will accrue approximately 700 patients (350 de novo, 350 established) anticipating 90% retention in the de novo cohort (85% established) for follow-up at 1 year, leaving a minimum 525 patients for primary analyses. High retention will be supported through close follow-up, mailed reminders, birthday cards, and a newsletter. Given the clinical follow-up necessary for KT recipients, we are confident we will achieve this goal.

Regimen adherence at one year is the primary outcome of interest for Aim 1, with Rx knowledge and individual adherence measures also of primary interest. Secondary outcomes include quality of life (PROMIS outcomes and FKSI) and the clinical outcomes of change in eGFR, and any transplant-related re-hospitalization. Blood pressure control in those taking anti-hypertensive medications will also be examined. Relationships between

adherence and potential confounders (age, comorbidity, cognitive ability, regimen complexity, internet use, dose of intervention, etc.) will also be examined. For all outcomes, we will use generalized linear models (GLMs), adjusted for confounders and study site, specifying the logit link function for binary outcomes and identity link for continuous outcomes (quality of life, change in eGFR, SBP). Treatment group will be the independent variable of primary interest, with usual care specified as reference group. We will also include time since transplant at baseline (in months), baseline value of the outcome, and any potential confounding covariates noted in bivariate analysis. For outcomes measured per medication, a generalized estimating equation (GEE) approach will be employed to adjust standard errors for within-patient correlation. Should TAKE IT have an effect on outcomes, secondary analyses will examine if any of the potential confounders considered exhibit any effect modification.

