### Aim 2.

Generalized linear mixed models (GLMMs) will be used to examine intervention effects over the course of the study. Link functions will be included as described above for the GLM models. Adherence concerns may differ in the two cohorts, thus separate models will be employed for each cohort (de novo, established). Treatment group will be the independent variable of primary interest, modeled as a fixed effect with the usual care group specified as reference group. We will also include fixed effects for site (NU, Mayo), time since transplant (in months), and potential confounding covariates noted in bivariate analyses. Random participant effects for each participant will be included to account for repeated measurements nested within each participant (assuming a compound symmetry, although we will fit autoregressive structures as well, comparing fit using AIC and BIC criterion). Outcomes recorded at each interview will be analyzed by visit whereas adherence measured by tacrolimus levels, along with blood pressure control will be analyzed in 6-month intervals as described above. A time-since-transplant-by-arm interaction term will be included to examine if outcome trajectories/slopes over time differ by study arm. Since prescription knowledge and adherence will be assessed for each medication, 2-level GLMM will be used for these outcomes with medications nested in participants. For  $\Delta$  eGFR and re-hospitalization outcomes, GLM models will be used since outcomes over 2 years are summarized in a single measurement. In the de novo cohort, change in eGFR from transplant to 2 years post-transplant and # hospitalizations (any hospitalization, if rare) within 2 years post-transplant will be modeled. For the established cohort, the time period for the both measures will span from transplant to 2-year study visit. It is possible those who do not complete the 2-year visit will differ in important characteristics (e.g. cognition, comorbidity), which could bias results. We will use collected data at prior interviews to understand the extent that individuals who complete follow-up differ from those who do not. If differences are found, pattern-mixture models will be employed by classifying participants' drop-out type or pattern (e.g. completed, refused, lost to follow up, death). This variable will then be added to mixed effects models to account for differences.

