*Power Calculation.* The sample size calculation was based on the availability of 700 transplant patients estimated by the number of transplants conducted in 2012-2014 across the two sites. With the sample size set at 610 accounting for 85-90% retention at 1 year, we present the minimum differences we will be able to detect between the intervention and usual care arms for each outcome of interest. For the main outcome of medication adherence, we estimate 45% of the sample to be non-adherent using the composite score described above taking estimates for each individual measure into account. We will have sufficient power ( $\geq 80\%$ ) to detect differences of 11% in the entire sample assuming a 5% Type I error rate. Should TAKE IT be associated with potential confounders, calculations show that an R-squared of 0.2 between predictors (a conservatively high estimate under randomization), we would still maintain 70% power to detect the 11% difference. Although adjusting for confounders would decrease variability in adherence, and increase power. Detectable differences for individual adherence measures along with estimates and effect sizes for other outcomes of interest are listed in Table 5.

Table 5. Detectable Differences in Health Outcomes between Study Arms at 1 Year

Outcome	Total (n=610) 305/arm		De Novo (n=270) 135/arm		Established (n=340) 170/arm	
	Usual Care Estimate	Minimum Difference	Usual Care Estimate	Minimum Difference	Usual Care Estimate	Minimum Difference
Primary Outcomes						
Rx Knowledge, %	50	11.3	60	15.9	45	15.1
Rx Non-adherence, %	45	11.0	35	15.2	50	15.0
Self-report, %	35	10.3	29	14.1	44	14.6
Objective (pill count), %	45	11.1	35	11.3	50	15.0
Claims (PDC), %	30	9.8	23	12.7	38	14.0
Biologic (SD Tacrolimus), %	40	10.8	30	14.3	45	14.7
Secondary Outcomes						
Quality of life, mean(SD)	46.2 (9.0)	2.0	45.8 (7.2)	2.5	49.5 (9.0)	2.7
Clinical outcomes						
$\Delta$ eGFR, mean(SD)*	-5.8 (9.0)	2.9	-3.0 (11.0)	3.8	-8.0 (15.0)	4.6
Re-hospitalizations, %	40	10.8	32	14.6	47	14.8
Systolic BP, mean(SD)**	136.7 (8.3)	2.2	138.3 (12.9)	5.1	135.0 (7.9)	2.8

\* $\Delta$  eGFR estimates over 2 years

[figure not shown]
\*\*estimate 75% of cohort has hypertension (Total: n=458, 229/arm; De Novo: n=202, 101/arm; Established: n=256, 128/arm)

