*Exploratory Analyses.* A single measurement for each exploratory transplant related clinical outcome (i.e. acute rejection, toxicity, infection) will be modeled at the end of the study indicating the total number of occurrences (or any for rare outcomes) over the course of the study using GLM models as described above. We recognize we likely will not have sufficient power to find differences in these outcomes. Intervention effects on blood pressure and glycemic control will be examined among those with diabetes and/or hypertension.

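### Aim 2 hospitalisation counts and exploratory event totals have no count model or time at risk; hospitalisation windows start before randomisation; toxicity has no onset rule for hypertension

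*Combined protocol and SAP*

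**What the plan says.** - **Exploratory outcomes** (section 11.1, Exploratory Analyses). Acute rejection, toxicity and infection each become a single measurement per patient, "indicating the total number of occurrences (or any for rare outcomes) over the course of the study using GLM models as described above".
- **Links** (section 11.1, Aim 1). The models are described as "specifying the logit link function for binary outcomes and identity link for continuous outcomes (quality of life, change in eGFR, SBP"). Aim 2 adds only this: "Link functions will be included as described above for the GLM models". Counts are not mentioned in either place.
- **Hospitalisation** (section 11.1, Aim 2). For the de novo cohort the number of "hospitalizations (any hospitalization, if rare) within 2 years post-transplant will be modeled". The other cohort has its own window, which also opens at transplant but closes at a study visit: "For the established cohort, the time period for the both measures will span from transplant to 2-year study visit". Aim 1 uses a different, binary outcome: any transplant-related re-hospitalisation.
- **Incomplete follow-up.** Aim 1 expects 90% (de novo) and 85% (established) retention at 1 year. Section 13 withdraws patients who stay unresponsive for 6 months and keeps the data gathered until then. The pattern-mixture remedy in Aim 2 is a variable added to mixed effects models.
- **Toxicity** (section 8.4). It is defined as "related to CNI medications (hypertension; neuro-toxic events"). The Table 5 footnote for systolic blood pressure reads "estimate 75% of cohort has hypertension".
- **Status.** Hospitalisation is secondary. Rejection, toxicity and infection are exploratory, and the plan concedes that power for them is probably insufficient.

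**The concern.** An event total depends on how long the patient was watched. A patient who dies or is lost at month 6 contributes a smaller total than one followed to month 24, and nothing in these models tells them apart. The plan recognises that non-completers could bias results, but its remedy does not reach the single-measurement GLMs used for events. Time since transplant at baseline is a covariate, but it is fixed at entry and cannot reflect later death or dropout.

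Two further features can hide a real effect even when loss is balanced. Hospitalisations before randomisation enter the Aim 2 count. Hypertension present before randomisation could enter the toxicity count, because no rule excludes it.

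At stake are the 2-year hospitalisation comparison and the three exploratory safety and graft outcomes. The primary adherence outcome is not touched.

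**Working it through.** **1. The plan's own figure.** Table 5 gives a re-hospitalisation rate of 40% and a minimum difference of 10.8 points at 305 per arm. Two-proportion test, pooled variance, two-sided 5%, reduction from 0.40 to 0.292, mean 0.346:

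- null SE = √(2 × 0.346 × 0.654 / 305) = 0.0385
- alternative SE = √((0.40 × 0.60 + 0.292 × 0.708) / 305) = 0.0383
- z = (0.108 − 1.96 × 0.0385) / 0.0383 = 0.85, so power is 0.80

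The de novo and established entries (14.6 and 14.8 points) also give 0.80. Table 5 therefore reproduces, but as a binary comparison at 1 year. It does not describe the 2-year count. At an assumed 40%, hospitalisation is not rare, so the count version would apply.

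**2. Time at risk.** If a fraction d of an arm drops out at uniformly spread times, mean observed time is 1 − d/2 of the full period. With no true effect, the ratio of mean counts is then:

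- 15% loss in both arms: 0.925 / 0.925 = 1.00
- 10% usual care, 20% TAKE IT: 0.90 / 0.95 = 0.947
- 5% usual care, 30% TAKE IT: 0.85 / 0.975 = 0.872

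Simulation (assumptions: 350 per arm, 0.3 events per year, 24 months from randomisation, gamma-Poisson counts with shape 1, time since transplant as covariate, 1,000 runs). Entries in the three model columns are rejection rates.

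| True ratio | Loss, usual care / TAKE IT | Identity link, no exposure | Logit, any event | Negative binomial, offset | Mean ratio without / with offset |
|---|---|---|---|---|---|
| 1.0 | 15% / 15% | 0.045 | 0.056 | 0.038 | 1.01 / 1.00 |
| 1.0 | 10% / 20% | 0.071 | 0.077 | 0.055 | 0.96 / 1.00 |
| 1.0 | 5% / 30% | 0.168 | 0.182 | 0.056 | 0.88 / 1.01 |
| 0.7 | 15% / 15% | 0.727 | 0.563 | 0.727 | 0.71 / 0.70 |
| 0.7 | 10% / 20% | 0.847 | 0.707 | 0.739 | 0.67 / 0.70 |

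Monte Carlo error at a 5% rate is √(0.05 × 0.95 / 1000) = 0.7 points. The 0.847 in the last row is not a gain: the unadjusted model overstates the effect (0.67 for a true 0.70).

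A second set-up (305 per arm, mean 0.8 events over 2 years, shape 0.6) compared the identity link with the offset model:

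- equal loss, no effect: 0.045 against 0.048
- equal loss, true ratio 0.7: 0.65 against 0.68
- 5% versus 30% loss, no effect: 0.155 against 0.058
- 20% loss in usual care, 10% in TAKE IT, true ratio 0.7: power 0.53 against 0.67

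**3. Events before randomisation.** Section 3.2 admits patients from 5 weeks to 24 months after transplant. For an established patient with m months of prior time and a constant event rate, a true post-randomisation ratio of 0.75 becomes (m + 24 × 0.75) / (m + 24):

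- m = 6: 24 / 30 = 0.80
- m = 12: 30 / 36 = 0.833
- m = 24: 42 / 48 = 0.875

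For a de novo patient enrolled at 5 weeks (1.2 months), in a window closing 24 months after transplant, it is (1.2 + 22.8 × 0.75) / 24 = 0.763. The problem lies mainly in the established cohort.

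**4. Hypertension as toxicity.** 0.75 × 610 = 457.5, the 458 in the footnote. Suppose each of these patients contributed one pre-existing event, and other toxicity averaged 0.20 per patient in usual care and 0.10 in TAKE IT (assumed). The ratio of mean counts moves from 0.50 to (0.75 + 0.10) / (0.75 + 0.20) = 0.89. With 0.10 against 0.05 it is 0.80 / 0.85 = 0.94; with 0.30 against 0.15 it is 0.90 / 1.05 = 0.86. On the difference scale the 0.10 is unchanged, but the extra events add variance of 0.75 × 0.25 = 0.19 per patient.

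**The case against.** - **Randomisation balances time at risk.** This stands. With equal loss, type I error is nominal and power nearly the same under either model. A reader might infer that the event comparisons are biased as planned. The documents do not support that: retention is given by cohort, never by arm, and no 2-year figure appears.
- **The plan does not commit to an identity link for counts.** This also stands. Its list of continuous outcomes contains none, so the defect is an unspecified count model. In simulation the identity link cost little by itself.
- **Time since transplant is in the model.** Partly right. For established completers the hospitalisation window is that time plus 24 months (about 25 to 48), so its length is partly adjusted. Early death and dropout are not.
- **Events come from the EHR, so a missed interview need not end capture.** Plausible, and it would shrink the problem. Section 13 leaves open whether record review continues after withdrawal.
- **The simulations do not match the planned analysis.** Fair. They pool the cohorts, whereas Aim 2 models them separately. The bias in the ratio would be the same with fewer patients, but the type I inflation smaller. The second set-up spreads Table 5's 1-year 40% over 2 years and applies loss to a sample already net of loss.
- **A toxicity ceiling.** A reader might infer that any toxicity would sit near 80–85% in both arms. That does not follow: the plan reserves the any-event form for rare outcomes, limits toxicity to CNI-related events, and uses 75% only to size the blood pressure comparison. What remains is a missing onset rule.

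**Conclusion.** The point holds in conditional form. The Aim 2 hospitalisation count and the exploratory totals lack a count model and a time-at-risk term, and the plan's drop-out remedy does not cover them.

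- **Unequal loss.** No harm if loss is equal by arm. Under assumed unequal loss, type I error is about 7% (10% versus 20%) to 16–17% (5% versus 30%), against about 5–6% with the offset. A real benefit can equally be hidden when usual care loses more patients.
- **Pre-randomisation events.** This is the firmest part, because it follows from the stated windows and needs no imbalance. It assumes a constant rate; a higher rate soon after transplant would dilute more.
- **Toxicity.** Dilution is a risk created by an open definition, not a certainty.

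Aim 1's binary re-hospitalisation outcome is not affected by the link criticism. For rejection, toxicity and infection the impact is limited, since they are exploratory with low power conceded. For hospitalisation, a secondary outcome, the change is worth making before analysis.

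**What to change.** In section 11.1:

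1. Count hospitalisations, rejection, toxicity and infection from randomisation. Use earlier hospitalisations only as a baseline covariate.
2. Model totals by negative binomial regression with a log link and log(months observed) as offset, where observation ends at death, end of EHR follow-up or month 24. Fit within cohort for Aim 2. State whether EHR capture continues after a patient stops interviews.
3. Where an outcome is rare, use time to first event, or a complementary log-log link with the same offset.
4. Count hypertension as toxicity only if first recorded after randomisation in a patient without it at baseline. Report neurotoxic events separately.
5. Tabulate observed time and reason for ending by arm. The offset corrects for length of observation, not for dropout that is itself related to event risk.

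Aim 1 may keep the logit link for any re-hospitalisation, and Table 5 needs no change for this point.

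The cost is SAP wording plus one last-observed date per patient, which the EHR review that supplies the events should provide. Results become rate ratios instead of mean differences, and events between transplant and randomisation no longer count towards the outcome.

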**Aim 3.**

We will determine the extent to which the interventions were implemented as planned at each site in order to optimize the intervention for future dissemination opportunities. Mixed methods will be employed using a convergent parallel design to obtain data on intervention implementation (Figure 8). We will capture 4 data sources: 1) patient self-report, 2) EHR, 3) field notes, and 4) clinic staff. Patients receiving the TAKE IT strategy arm will be asked whether they received EHR materials and visited the portal. We will examine if receipt of EHR tools increased KT recipient knowledge and behaviors. At 12 and 24 month interviews, a random sample of 50 patients from the intervention arm will be asked additional, semi-structured questions to explore 1) personal challenges with regimen adherence, 2) perceived value of the EHR, SMS, and

Figure 8. Integration of Parallel Data Sources

\*Convergent parallel design adapted from Creswell & Clark, 2011

portal tools, 3) unmet needs and acceptability of other tools and approaches to support medication use. Interviews will be audio-recorded and transcribed. EHR data will capture whether patients actually receive EHR tools and if identified adherence concerns from the portal assessment generated a care alert, if a response was documented, and when. We will use field notes to monitor ongoing clinic changes. [name] will have monthly calls with clinic administrators to document any changes that might have occurred and when. This includes relevant changes to clinic staffing, workflow, EHR, or any significant event that could potentially alter delivery and subsequent effectiveness of the TAKE IT strategy. Discussions groups will be held with staff during business meetings to assess the intervention's impact on workflow. These will be audio-recorded.

*Analysis Plan.* Quantitative and qualitative findings will be merged to answer 1) whether the intervention was implemented as planned (e.g. fidelity), 2) from a user-perspective, do interventions require modification and how. In this approach, both analyses are conducted separately and merged for side-by-side data comparisons. For quantitative data (patient report, EHR data), frequencies will be generated to determine overall rate of perceived helpfulness of materials, receipt of materials, participation in the Web-based portal to report medication use, and the overall rate of EHR notifications. Although we expect a high fidelity level, if there are “glitches” that prevent TAKE IT from being implemented optimally, we will do an exploratory analysis to determine if fidelity rates had any association with improvement in outcomes. For qualitative data, we will review and explore the transcribed patient interviews and clinic staff discussions using content and ethnographic analysis led by Drs. [name], [name] and [name]. Predetermined categories will organize feedback from all users: patient, provider, clinic/health system. Within each of these categories we will use a predetermined coding approach to quantify the frequency of two subcategories: facilitating factors, and impeding factors (Figure 8). An additional layer within impeding factors would be whether factors are modifiable or not, and under facilitating factors, if they are replicable. Field notes and quantitative findings will be integrated. Transcribed interviews and field notes will be examined by Drs. [name], [name], & [name] independently. Analyses will be conducted with NVivo 10 (QSR International).

#### Aim 4.

[name], working with Drs. [name], [name], & [name] will directly measure and assess the costs of developing and running the TAKE IT Strategy. The incremental cost of TAKE IT will be estimated relative to usual care from the perspective of the two sites implementing these processes and tools. The primary costs of running TAKE IT technologies in the EHR involve the limited expenses around printing (printer ink, paper, staff time) as a result of generating MedSheets and the Medlist with the AVS (during clinic visits). SMS monthly costs will be easily documented as well as usage. However, we will include estimates for programming maintenance for OTTR and Cerner EHRs, and the portal. We will test the sensitivity of results to changes in maintenance requirements (in programmer hours). Development costs for software and other programming requirements will be separately tracked based on programmer hours. Staff costs (nurse coordinator, pharmacist, social worker, other clinicians, programmer) will be measured using tracked time spent on the intervention and wage estimates. We will test the sensitivity of operational costs to different assumptions about potential use of variable staff using different salaries but

assuming the same proficiency in terms of time required. We will also assess the sensitivity of estimates to different proficiency levels that could arise from learning by doing.

